12.3 Response Criteria for Patients with Solid Tumors

See the table in [section 8.0](#) for the schedule of tumor evaluations. Eligible patients must have measurable disease present at baseline and have had their disease re-evaluated after one dose of protocol therapy. In addition to the scheduled scans, a confirmatory scan should be obtained on the next consecutive cycle following initial documentation of objective response.

As outlined, patients will be assigned to one of the following categories for assessment of response: a) solid tumor (non-CNS) and measurable disease ([Section 12.4](#)); b) neuroblastoma with MIBG positive lesions ([Section 12.5](#)); c) CNS tumor ([Section 12.7](#)); and d) non-Hodgkin lymphoma/histiocytosis ([Section 12.8](#)). Note: Neuroblastoma patients who do not have MIBG positive lesions should be assessed for response as solid tumor patients with measurable disease.

Response and progression will be evaluated in this study using the revised Response Evaluation Criteria in Solid Tumors (RECIST) guideline (version 1.1).⁶² Key points are that 5 target lesions are identified and that changes in the *largest* diameter (unidimensional measurement) of the tumor lesions but the *shortest* diameter of malignant lymph nodes are used in the RECIST v 1.1 criteria.

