12.4.3 Overall Response Assessment

Table 1: For Patients with Measurable Disease (i.e., Target Disease)

Target Lesions	Non-Target Lesions	New Lesions	Overall Response	Best Overall Response when Confirmation is Required*
----------------	--------------------	-------------	------------------	--

CR	CR	No	CR	≥ 28 days Confirmation
CR	Non-CR/Non-PD	No	PR	≥ 28 days Confirmation
CR	Not evaluated	No	PR	
PR	Non-CR/Non-PD/not evaluated	No	PR	
SD	Non-CR/Non-PD/not evaluated	No	SD	documented at least once ≥ 28 days from baseline
PD	Any	Yes or No	PD	no prior SD, PR or CR
Any	PD**	Yes or No	PD	
Any	Any	Yes	PD	

* See RECIST 1.1 manuscript for further details on what is evidence of a new lesion.
 ** In exceptional circumstances, unequivocal progression in non-target lesions may be accepted as disease progression.

Note: Patients with a global deterioration of health status requiring discontinuation of treatment without objective evidence of disease progression at that time should be reported as "*symptomatic deterioration*." Every effort should be made to document the objective progression even after discontinuation of treatment.

Table 2: For Patients with Non-Measurable Disease (i.e., Non-Target Disease)

Non-Target Lesions	New Lesions	Overall Response
CR	No	CR
Non-CR/non-PD	No	Non-CR/non-PD*
Not all evaluated	No	not evaluated
Unequivocal PD	Yes or No	PD
Any	Yes	PD

* 'Non-CR/non-PD' is preferred over 'stable disease' for non-target disease since SD is increasingly used as an endpoint for assessment of efficacy in some trials so to assign this category when no lesions can be measured is not advised

Table 3: Overall Response for Patients with Neuroblastoma and Measurable Disease

CT/MRI	MIBG	Bone Scan	Bone Marrow	Catechol	Overall
PD	Any	Any	Any	Any	PD
Any	PD	Any	Any	Any	PD
Any	Any	PD	Any	Any	PD
Any	Any	Any	PD	Any	PD
SD	CR/PR/SD	Non-PD	Non-PD	Any	SD
PR	CR/PR	Non-PD	Non-PD	Any	PR
CR/PR	PR	Non-PD	Non-PD	Any	PR
CR	CR	Non-PD	Non-PD	Elevated	PR
CR	CR	CR	CR	Normal	CR

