12.5 Response Criteria for Neuroblastoma Patients with MIBG Positive Lesions

12.5.1 MIBG Positive Lesions

Patients who have a positive MIBG scan at the start of therapy will be evaluable for MIBG response. The use of ^{123}I for MIBG imaging is recommended for all scans. If the patient has only one MIBG positive lesion and that lesion was radiated, a biopsy must be done at least 28 days after radiation was completed and must show viable neuroblastoma.

12.5.2 The following criteria will be used to report MIBG response by the treating institution:

Complete response: Complete resolution of all MIBG positive lesions

Partial Response: Resolution of at least one MIBG positive lesion, with persistence of other MIBG positive lesions

Stable disease: No change in MIBG scan in number of positive lesions

Progressive disease: Development of new MIBG positive lesions

12.5.3 The response of MIBG lesions will be assessed on central review using the Curie scale¹⁴ as outlined below. Central review responses will be used to assess efficacy for study endpoint. See [Section 8.2](#) for details on transferring images to the Imaging Research Center.

NOTE: This scoring should also be done by the treating institution for end of course response assessments.

The body is divided into 9 anatomic sectors for osteomedullary lesions, with a 10th general sector allocated for any extra-osseous lesion visible on MIBG scan. In each region, the lesions are scored as follows. The **absolute extension score** is graded as:

[figure not shown]
0 = no site per segment,

1 = 1 site per segment,

2 = more than one site per segment,

3 = massive involvement (>50% of the segment).

The **absolute score** is obtained by adding the score of all the segments. See diagram of sectors below:

The **relative score** is calculated by dividing the absolute score at each time point by the corresponding pre-treatment absolute score. The relative score of each patient is calculated at each response assessment compared to baseline and classified as below:

1. **Complete response:** all areas of uptake on MIBG scan completely resolved. If morphological evidence of tumor cells in bone marrow biopsy or aspiration is present at enrollment, no tumor cells can be detected by routine morphology on two subsequent bilateral bone marrow aspirates and biopsies done at least 21 days apart to be considered a **Complete Response**.

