12.5.4 Overall Response Assessment

Table 4: Overall Response Evaluation for Neuroblastoma Patients and MIBG Positive Disease Only

If patients are enrolled without disease measurable by CT/MRI, any new or newly identified lesion by CT/MRI that occurs during therapy would be considered progressive disease.

MIBG	CT/MRI	Bone Scan	Bone Marrow	Catechol	Overall
PD	Any	Any	Any	Any	PD
Any	New Lesion	Any	Any	Any	PD
Any	Any	PD	Any	Any	PD
Any	Any	Any	PD	Any	PD
SD	No New Lesion	Non-PD	Non-PD	Any	SD
PR	No New Lesion	Non-PD	Non-PD	Any	PR
CR	No New Lesion	Non-PD	Non-PD	Elevated	PR
CR	No New Lesion	CR	CR	Normal	CR

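### For neuroblastoma that is both MIBG-positive and CT/MRI-measurable, the routing in Section 12.3 and the headings of Tables 3 and 4 disagree on which response table applies, so a stable CT mass with an MIBG response can be called SD or PR

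*Combined protocol and SAP*

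**What the plan says.** Section 12.3 states that "patients will be assigned to one of the following categories for assessment of response". The second category is "b) neuroblastoma with MIBG positive lesions", which points to Section 12.5 and makes no exception for patients who also have lesions measurable by CT or MRI. The Note that follows adds: "Neuroblastoma patients who do not have MIBG positive lesions should be assessed for response as solid tumor patients with measurable disease". No other neuroblastoma patient is named for the measurable-disease route in Section 12.4.

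There are two tables for overall response in neuroblastoma:

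- Section 12.4.3 holds "Table 3: Overall Response for Patients with Neuroblastoma and Measurable Disease". It combines CT/MRI response, MIBG response, bone scan, marrow and catecholamines.
- Section 12.5.4 holds "Table 4: Overall Response Evaluation for Neuroblastoma Patients and MIBG Positive Disease Only". Its lead-in concerns patients enrolled without CT/MRI-measurable disease, and its CT/MRI column records only whether a new lesion has appeared.

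Section 12.5 does not mention Table 3. On the MIBG reading itself, 12.5.3 says: "Central review responses will be used to assess efficacy for study endpoint".

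Under 4.1.4, measurable disease is the normal entry requirement and MIBG-only neuroblastoma is an added route, so patients with both kinds of disease can enrol. A responder has a best response of PR or CR (11.4). Since Amendment #5A, the two primary cohorts are pooled into one set of 20, with success at 3 or more responses (11.3.1).

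**The concern.** A patient with both kinds of disease is placed by the routing text in a section whose only overall table was not written for that patient. The table that was written for that patient sits in a section to which the Note sends only MIBG-negative neuroblastoma. Yet Table 3 has MIBG entries of CR, PR and SD, which can arise only in patients who were MIBG-positive.

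The choice of table matters because the two can give the same scans different responder status. Primary success turns on a count of three, and an unstated choice between tables could be made after the scans are known.

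**Working it through.** **1. The plan's own design figures.** Inputs from 11.3 and 11.3.1: N = 20, success at 3 or more responses, null rate 5%, target rate 25%, alpha 10%, power 90%. Exact binomial tails:

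- Alpha: P(X ≥ 3 | 20, 0.05) = 1 − (0.35849 + 0.37735 + 0.18868) = 0.0755.
- Power: P(X ≥ 3 | 20, 0.25) = 0.9087.

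N = 20 with 3 responses is the smallest single-stage design that meets both targets. The design figures are sound, with 10% acting as a ceiling on alpha.

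**2. The two tables side by side.** Four CT/MRI categories crossed with four MIBG categories give 16 combinations. Take no new CT/MRI lesion, and no progression on bone scan or in marrow.

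| CT/MRI | MIBG | Table 3 | Table 4 |
|---|---|---|---|
| SD | PR | SD | PR |
| SD | CR | SD | PR or CR |
| PR or CR | SD | no row | SD |
| PD by growth | SD, PR or CR | PD | SD; PR; PR or CR |

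The rows behind the first conflict are, in Table 3, "SD CR/PR/SD Non-PD Non-PD Any SD" and, in Table 4, "PR No New Lesion Non-PD Non-PD Any PR". Where Table 4 gives PR or CR, the bone scan, marrow and catecholamine columns decide between them.

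The lines above cover 2 + 2 + 3 = 7 of the 16 combinations. In the other nine the tables agree on responder status. (CT PR with MIBG CR is PR in Table 3 and PR or CR in Table 4, a responder either way.) The seven sort as follows:

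- Three have CT/MRI growth to PD. Section 12.2 settles these: progression in an established lesion is progressive disease whatever other lesions do.
- Two (CT/MRI SD with MIBG PR or CR) are true conflicts in responder status, and 12.2 does not reach them.
- Two (CT/MRI PR or CR with MIBG SD) have no row in Table 3, so they cannot be classified there.

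**3. Effect on the decision.** Two responders in 20 is 10%, a failure (Wilson 90% interval 3.4% to 26.2%). Three in 20 is 15%, a success (6.2% to 32.2%). One conflicting patient is enough to move between them.

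**4. Illustration.** Assume exactly one conflicting patient, with the other 19 responding independently at 5%.

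- Called PR, two more responders are needed: P(X ≥ 2 | 19, 0.05) = 1 − 0.37735 − 0.37735 = 0.2453.
- Called SD, three are needed: P(X ≥ 3 | 19, 0.05) = 0.0665.

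The proper comparison is 24.5% against 6.7%, since both hold that one patient fixed. The 7.5% from step 1 is the wrong comparator because it lets all 20 vary.

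**The case against.** The strongest defence is that the table headings already settle the matter. Table 4 is limited by both title and lead-in to patients without CT/MRI-measurable disease. Table 3 is titled for measurable disease and has an MIBG column. Read by heading, the tables do not overlap, and CT/MRI SD with MIBG PR is SD. A patient with both kinds of disease also fits the first category in 12.3 (non-CNS solid tumor, measurable), and the Note does not bar that patient from 12.4. Section 12.6.1 expects tumor measurements and MIBG to be used together.

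Most of this stands. Table 3 is the likelier intention, and it would be too strong to say that 12.3 unequivocally sends every MIBG-positive patient to 12.5. But the inference from the headings runs against the category that names MIBG-positive neuroblastoma and against the Note, and nothing says which prevails. Central review (11.5, 12.3.1.1) and the requirement for two determinations (12.9) do not help: they settle the readings and their confirmation, not which table combines them.

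A reader might also infer that a patient whose measurable tumor is growing could be scored a responder and progression-free through Table 4. The documents do not support that, because 12.2 gives progression in any established lesion precedence.

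Nor do they support a claim that the trial's error rate is materially inflated. They give no count of such patients and no rate of discordant MIBG and CT/MRI responses. The sequencing data in 2.1 place 55% of pathway alterations in brain tumors and 31% in sarcomas. That leaves 100 − 55 − 31 = 14% for all other histologies, or 0.14 × 20 = 2.8 patients if enrolment followed that mix, and neuroblastoma is not named among them. That one patient can swing the result is true of any 3-of-20 rule; the point here is only that the table choice is not fixed in advance.

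**Conclusion.** The point holds in a limited form. For neuroblastoma with both MIBG-positive and CT/MRI-measurable disease, the routing in 12.3 and the headings of Tables 3 and 4 conflict, and no rule says which governs. Responder status differs when CT/MRI is stable and MIBG shows PR or CR. Table 3 also has no row for CT/MRI PR or CR with MIBG SD.

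The effect is at most one responder per affected patient, which is enough to turn 2/20 into 3/20. The 24.5% against 6.7% is an illustration that assumes exactly one conflicting patient and 5% response in the rest; it is not an estimate of the trial's error rate. The number of affected patients may be zero. The sample size and decision rule are not in error.

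**What to change.** Reconcile 12.3 with the protocol's own table titles before final response calls:

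- **Measurable by CT/MRI, MIBG-positive or not:** use Table 3. When MIBG is positive, enter the central Curie category from 12.5.3 in the MIBG column. When it is negative, use a stated entry. Point the Note in 12.3 to Table 3, because Table 1 has no marrow, bone-scan or catecholamine column.
- **MIBG-positive without CT/MRI-measurable disease:** use Table 4.
- **Category b) in 12.3:** reword to cover MIBG-positive lesions without measurable disease, and cross-refer from 12.5 to Table 3.
- **Table 3:** add the missing row for CT/MRI PR or CR with MIBG SD and state its overall category. Without it, the new routing would leave some patients unclassifiable for the primary endpoint.

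The cost is protocol wording and a check of how any neuroblastoma patients already enrolled were classified. N, the decision rule and data collection do not change. The one downside is that a patient with an MIBG response but a stable CT mass would not count as a responder.

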12.3.1 Definitions

12.3.1.1 Evaluable for objective response:

Eligible patients who receive at least one dose of protocol therapy will be considered evaluable for response. Evaluable patients who demonstrate a complete or partial response confirmed by central review before receiving non-protocol anti-cancer therapy will be considered a responder. All other evaluable patients will be considered non-responders.

12.3.1.2 Evaluable Non-Target Disease Response:

Eligible patients who have evaluable but not measurable disease and have received at least one dose of protocol therapy will be considered evaluable for non-target disease. The response assessment is based on

the presence, absence, or unequivocal progression of the lesions.

12.3.2 Disease Parameters

12.3.2.1 **Measurable disease:** Measurable lesions are defined as those that can be accurately measured in at least one dimension (longest diameter to be recorded) as ≥ 20 mm by chest x-ray, as ≥ 10 mm with CT scan, or ≥ 10 mm with calipers by clinical exam. All tumor measurements must be recorded in millimeters (or decimal fractions of centimeters).

Note: Tumor lesions that are situated in a previously irradiated area might or might not be considered measurable. If the investigator thinks it appropriate to include them, the conditions under which such lesions should be considered must be defined in the protocol.

12.3.2.2 **Malignant lymph nodes:** To be considered pathologically enlarged and measurable, a lymph node must be ≥ 15 mm in short axis when assessed by CT scan (CT scan slice thickness no greater than 5 mm). At baseline and in follow-up, only the short axis will be measured and followed.

12.3.2.3 **Non-measurable disease:** All other lesions (or sites of disease), including small lesions (longest diameter < 10 mm or pathological lymph nodes with ≥ 10 to < 15 mm short axis), are considered non-measurable disease. Bone lesions, leptomeningeal disease, ascites, pleural/pericardial effusions, lymphangitis cutis/pulmonitis, inflammatory breast disease, and abdominal masses (not followed by CT or MRI), are considered as non-measurable.

Note: Cystic lesions that meet the criteria for radiographically defined simple cysts should not be considered as malignant lesions (neither measurable nor non-measurable) since they are, by definition, simple cysts. 'Cystic lesions' thought to represent cystic metastases can be considered as measurable lesions, if they meet the definition of measurability described above. However, if non-cystic lesions are present in the same patient, these are preferred for selection as target lesions.

12.3.2.4 **Target lesions:** All measurable lesions up to a maximum of 2 lesions per organ and 5 lesions in total, representative of all involved organs, should be identified as target lesions and recorded and measured at baseline. Target lesions should be selected on the basis of their size (lesions with the longest diameter), be representative of all involved organs, but in addition should be those that lend themselves to reproducible repeated measurements. It may be the case that, on occasion, the largest lesion does not lend itself to reproducible measurement in which circumstance the next largest lesion that can be measured reproducibly should be selected. A sum of the diameters (longest for non-nodal lesions, short axis for nodal lesions) for all target lesions will be calculated and reported as the baseline sum diameters. If lymph nodes are to be included in the sum, then only the short axis is added into the sum. The baseline sum diameters will be used as reference to further characterize any objective tumor regression in the measurable dimension of the

disease.

12.3.2.5 **Non-target lesions:** All other lesions (or sites of disease) including any measurable lesions over and above the 5 target lesions should be identified as non-target lesions and should also be recorded at baseline. Measurements of these lesions are not required, but the presence, absence, or in rare cases unequivocal progression of each should be noted throughout follow-up.

12.3.3 **Methods for Evaluation of Measurable Disease**

All measurements should be taken and recorded in metric notation using a ruler or calipers.

The same method of assessment and the same technique should be used to characterize each identified and reported lesion at baseline and during follow-up. Imaging-based evaluation is preferred to evaluation by clinical examination unless the lesion(s) being followed cannot be imaged but are assessable by clinical exam.

12.3.3.1 **Clinical lesions:** Clinical lesions will only be considered measurable when they are superficial (e.g., skin nodules and palpable lymph nodes) and ≥ 10 mm diameter as assessed using calipers (e.g., skin nodules). In the case of skin lesions, documentation by color photography, including a ruler to estimate the size of the lesion, is recommended.

12.3.3.2 **Chest x-ray:** Lesions on chest x-ray are acceptable as measurable lesions when they are clearly defined and surrounded by aerated lung. However, CT is preferable.

12.3.3.3 **Conventional CT and MRI:** This guideline has defined measurability of lesions on CT scan based on the assumption that CT slice thickness is 5 mm or less. If CT scans have slice thickness greater than 5 mm, the minimum size for a measurable lesion should be twice the slice thickness. MRI is also acceptable in certain situations (e.g. for body scans). Ideally, the same type of scanner should be used and the image acquisition protocol should be followed as closely as possible to prior scans.

12.3.3.4 **PET-CT:** At present, the low dose or attenuation correction CT portion of a combined PET-CT is not always of optimal diagnostic CT quality for use with RECIST measurements. However, if the site can document that the CT performed as part of a PET-CT is of identical diagnostic quality to a diagnostic CT (with IV and oral contrast), then the CT portion of the PET-CT can be used for RECIST or International Pediatric non-Hodgkin Lymphoma Response Criteria measurements and can be used interchangeably with conventional CT in accurately measuring cancer lesions over time. Note, however, that the PET portion of the CT introduces additional data which may bias an investigator if it is not routinely or serially performed.

12.3.3.5 **Tumor markers:** Tumor markers alone cannot be used to assess response. If markers are initially above the upper normal limit, they must normalize for a patient to be considered in complete clinical response.

12.3.3.6 **Cytology, Histology:** These techniques can be used to differentiate between partial responses (PR) and complete responses (CR) in rare cases (e.g., residual lesions in tumor types, such as germ cell tumors, where known residual benign tumors can remain).

Cytology should be obtained if an effusion appears or worsens during treatment when the measurable tumor has met criteria for response or stable disease.

12.3.3.7 **FDG-PET:** While FDG-PET response assessments need additional study, it is sometimes reasonable to incorporate the use of FDG-PET scanning to complement CT scanning in assessment of progression (particularly possible 'new' disease). New lesions on the basis of FDG-PET imaging can be identified according to the following algorithm:

- a. Negative FDG-PET at baseline, with a positive FDG-PET at follow-up is a sign of PD based on a new lesion.
- b. No FDG-PET at baseline and a positive FDG-PET at follow-up: If the positive FDG-PET at follow-up corresponds to a new site of disease confirmed by CT, this is PD. If the positive FDG-PET at follow-up is not confirmed as a new site of disease on CT, additional follow-up CT scans are needed to determine if there is truly progression occurring at that site (if so, the date of PD will be the date of the initial abnormal FDG-PET scan). If the positive FDG-PET at follow-up corresponds to a pre-existing site of disease on CT that is not progressing on the basis of the anatomic images, this is not PD.

Note: A 'positive' FDG-PET scan lesion means one that is FDG avid with an uptake greater than twice that of the surrounding tissue on the attenuation corrected image.

For patients with a positive PET scan at diagnosis, PET can be used to follow response in addition to a CT scan using the International Pediatric non-Hodgkin Lymphoma Response Criteria.⁶³

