4.1 Inclusion Criteria

4.1.1 APEC1621SC: Patient must have enrolled onto APEC1621SC and must have been given a treatment assignment to MATCH to APEC1621D based on the presence of an actionable mutation as defined in APEC1621SC. Examples of actionable mutations for APEC1621D are listed in [Appendix VII-A](#) and [Appendix VII-B](#).

Note that treatment assignment may be to primary cohort A for patients with TSC1 or TSC2 loss of function mutations or primary cohort B for patients with other PI3K/MTOR pathway mutations (see [section 11.3.1](#)).

4.1.2 Age: Patients must be \geq than 12 months and \leq 21 years of age at the time of study enrollment.

4.1.3 BSA: Patients accruing to Dose Level 1 must have a body surface area ≥ 0.52 m² at the time of study enrollment. Patients accruing to Dose Level 2 must have a body surface area ≥ 0.37 m² at the time of study enrollment. Patients accruing to Dose Level -1 must have a body surface area ≥ 0.75 m² at the time of study enrollment.

4.1.4 Disease Status:

Patients must have radiographically **measurable** disease (See [section 12.0](#)) at the time of study enrollment. Patients with neuroblastoma who do not have measurable disease but have MIBG+ evaluable disease are eligible. Measurable disease in patients with CNS involvement is defined as any lesion that is at minimum 10 mm in one dimension on standard MRI or CT.

Note: The following do not qualify as measurable disease:

- malignant fluid collections (e.g., ascites, pleural effusions)
- bone marrow infiltration except that detected by MIBG scan for neuroblastoma
- lesions only detected by nuclear medicine studies (e.g., bone, gallium or PET scans) except as noted for neuroblastoma
- elevated tumor markers in plasma or CSF
- previously radiated lesions that have not demonstrated clear progression post radiation
- leptomeningeal lesions that do not meet the measurement requirements for RECIST 1.1.
- bone lesions without an associated soft tissue mass ≥ 10 mm in greatest diameter. Bone lesions with an associated soft tissue mass ≥ 10 mm in greatest diameter imaged by CT or MRI are considered measurable.

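### For non-CNS solid tumours, a bone lesion with a soft tissue mass of at least 10 mm is measurable at entry (4.1.4) but falls in an unqualified non-measurable list for response (12.3.2.3), so whether a PR can be scored depends on which section is applied

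*Combined protocol and SAP*

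**What the plan says.** **Entry.** Section 4.1.4 requires measurable disease and refers to section 12 for what that means. It then gives its own rule for bone: "Bone lesions with an associated soft tissue mass ≥ 10 mm in greatest diameter imaged by CT or MRI are considered measurable". Among the things that do not qualify, it lists "leptomeningeal lesions that do not meet the measurement requirements for RECIST 1.1", so a leptomeningeal lesion that does meet those requirements is not ruled out.

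**Response.** Section 12.3.2.1 opens: "Measurable lesions are defined as those that can be accurately measured in at least one dimension (longest diameter to be recorded"), with a threshold of 10 mm on CT and no anatomical site excluded. Section 12.3.2.3 then defines non-measurable disease, beginning "All other lesions (or sites of disease), including small lesions". Its second sentence lists sites that count as non-measurable, starting with "Bone lesions, leptomeningeal disease, ascites, pleural/pericardial effusions, lymphangitis cutis/pulmonitis, inflammatory breast disease". Neither bone lesions nor leptomeningeal disease is qualified there.

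**Scoring.** Only measurable lesions can be target lesions (12.3.2.4). PR in solid tumours is a fall of at least 30% in the target-lesion sum (12.4.1). Where disease is non-measurable, 12.4.3 supplies Table 2, headed "For Patients with Non-Measurable Disease (i.e., Non-Target Disease"). Its outcomes are CR, non-CR/non-PD, not evaluated and PD.

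**Denominator.** Under 11.5 and 12.3.1.1, every eligible patient with at least one dose is evaluable. Anyone without a centrally confirmed CR or PR is a non-responder.

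**The concern.** A patient can be admitted under 4.1.4 because the soft tissue mass is measurable, and then be read under 12.3.2.3 as having no measurable disease. If that lesion is the patient's only disease, a large but incomplete shrinkage of the mass is a PR on one reading and a non-response on the other. Section 4.1.4 sends the reader to section 12 for measurability, so the reference leads to text that disagrees with it.

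The primary decision rests on 3 responses among 20 evaluable patients (11.3.1, cohorts combined as of Amendment 5A), so a single PR scored differently can change the conclusion. The literal reading of 12.3.2.3 errs in one direction only: it can hide activity but cannot create it. Final response status comes from central review, so the reading adopted there decides the result.

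**Working it through.** **1. Reproduce the design.** Inputs from 11.3 and 11.3.1: N = 20, success at 3 or more responses, null rate 5%, target rate 25%, alpha 10%, power 90%.

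P(X ≥ 3) = 1 − Σ(x = 0 to 2) C(20, x) pˣ (1 − p)²⁰⁻ˣ

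- At p = 0.25: 1 − (0.0032 + 0.0211 + 0.0669) = 0.909. The stated 90% power is reproduced.
- At p = 0.05: 0.0755. The stated 10% is the ceiling and the attained value is 7.5%.

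**2. Compare the rules for one patient.** Take a non-CNS solid-tumour patient whose only disease is a bone lesion with a soft tissue mass of 10 mm or more.

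| Step | Mass read as measurable (4.1.4, or 12.3.2.1 on CT) | Bone list in 12.3.2.3 applied literally |
|---|---|---|
| Target lesion | Yes | No |
| Outcomes that count as response | CR or PR | CR only (Table 2) |
| In denominator | Yes | Yes |

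**3. Illustrate the size.** The documents do not give the number k of such patients among the 20, so k is an assumption, as are the CR rates used for them. Let the other 20 − k respond at 25%.

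(a) Worst case, no CR in the k patients: X ~ Binomial(20 − k, 0.25), and the success probability is P(X ≥ 3).

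(b) CR at an assumed 5% in the k patients: A ~ Binomial(20 − k, 0.25), B ~ Binomial(k, 0.05), and the success probability is P(A + B ≥ 3).

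| k | Average response rate in (a) = 0.25 × (20 − k)/20 | (a) no CR | (b) CR 5% |
|---|---|---|---|
| 0 | 25.0% | 90.9% | 90.9% |
| 1 | 23.75% | 88.9% | 89.3% |
| 2 | 22.5% | 86.5% | 87.4% |
| 4 | 20.0% | 80.3% | 82.8% |

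Hand check at k = 1. With n = 19, P(A = 2) = 171 × 0.25² × 0.75¹⁷ = 0.0803 and P(A ≥ 3) = 0.8887. Case (b) is therefore 0.8887 + 0.05 × 0.0803 = 0.893.

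Under the null, with 5% response in the rest and none in the k patients, the success probability falls from 7.5% to 4.3% at k = 4. This confirms that the error is toward missing activity.

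**4. How close the rule is to one patient.** At a 25% rate, exactly 3 responses in 20 has probability C(20, 3) × 0.25³ × 0.75¹⁷ = 1140 × 0.015625 × 0.00752 = 13.4%. In that outcome, one PR rescored as non-response reverses the decision.

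**The case against.** **A reader might infer that these patients have no route to a partial response.** The documents do not establish that. Section 12.3.2.1 makes a lesion of 10 mm or more on CT measurable whatever its site, and 12.3.2.3 by its opening words covers what is left over. On that reading the mass is already measurable, can be a target under 12.3.2.4, and PR is available. Section 4.1.4 is also the more specific rule for this lesion, and 12.3 provides no separate category for non-CNS solid tumours with only non-measurable disease, apart from the neuroblastoma exception ("Patients with neuroblastoma who do not have measurable disease but have MIBG+ evaluable disease are eligible"). All of this stands.

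It does not settle the matter. The second sentence of 12.3.2.3 sorts by site: ascites and effusions in it do not become measurable by being large. One item, abdominal masses, carries an imaging qualifier and bone lesions carry none. Section 12.3.2.1 names chest x-ray, CT and calipers, while 4.1.4 also admits a mass seen on MRI, which 12.3.3.3 accepts only in some situations. Two careful readers could differ.

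**A reader might infer that such patients are certain non-responders.** They are not, because Table 2 keeps CR.

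**A reader might extend the leptomeningeal mismatch to CNS tumours.** Those follow 12.7, with its own 10 mm definition and its own PR rule. MIBG-positive neuroblastoma (12.5) and lymphoma or histiocytosis (12.8) also have separate criteria.

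**A reader might take k from the background figures.** The 24% in section 2.1 is the pathway mutation frequency within osteosarcoma, and the 31% is the share of sarcomas among altered tumours. Neither is the share of enrolled patients with bone disease and no other measurable lesion. The same section puts 55% of the alterations in brain tumours, which 12.3.2.3 does not govern.

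**Conclusion.** The two sections conflict on bone lesions with a soft tissue mass of at least 10 mm. The conflict reaches the primary endpoint for non-CNS solid-tumour patients who have no other measurable lesion. Under the literal wording of 12.3.2.3 a true PR in such a patient is scored as non-response; under 4.1.4 it is not. The leptomeningeal mismatch is real within the same limits.

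The loss is about 2 percentage points of power for one affected patient (90.9% to 88.9%) and about 11 for four (90.9% to 80.3%) in the worst case. It is smaller if some of these patients reach CR. These figures rest on an assumed k, on a 25% response rate in the other patients, and on every affected patient being read literally under 12.3.2.3. They illustrate the exposure and do not estimate it.

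A reader might conclude that the stated sample size or power is in error. It is not: N = 20, the cutoff of 3 and the 90% power all reproduce. The text should still be corrected, because a stated rule applied as written can change a decision that turns on three responses.

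**What to change.** Before final central review, make section 12 agree with 4.1.4:

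- In 12.3.2.3, replace the bone item with: *bone lesions without an associated soft tissue mass of at least 10 mm on CT or MRI*.
- In 12.3.2.3, restrict the leptomeningeal item to lesions that fail the RECIST 1.1 measurement requirements, as 4.1.4 already does.
- In 12.3.2.4, add one sentence saying that for an eligible bone lesion the soft tissue component is the target and is what is measured.

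The cost is two reworded items and one added sentence. Eligibility, scan schedule, sample size and decision rule do not change. Settling the wording before final central review also means that neither reading can be chosen once the responses are known.
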